1.5.3.1 Primary endpoint

See Section 1.2 for the definition of the primary endpoint.

For the primary objective of the trial, the primary estimand is the difference in means of the primary efficacy endpoint of 400 mg intravenous neridronic acid compared to placebo for all allocated and treated subjects. This treatment policy or de facto estimand measures the effect of neridronic acid regardless of adherence to treatment or protocol.

The primary estimand will be estimated by the analysis of the primary efficacy endpoint for the Full Analysis Set. The primary analysis will fit a mixed model for repeated measures (MMRM) to the change from baseline in the average pain intensity scores from Week 1 to Week 12 recorded once daily in the electronic diary, including the covariate baseline pain intensity score, and the factors geographic region, week, treatment, and treatment-by-week interaction as fixed effects, and an unstructured covariance matrix to model the covariance structure of the repeated measurements.

The primary efficacy analysis will be performed using the contrast, i.e., the mixed model Wald test, of neridronic acid 400 mg versus placebo at Week 12 of the treatment, week and treatment-by-week interaction term of the mixed effects model described above. Model-based parameter estimates, standard errors, 95% confidence intervals, and p-values will be tabulated. This analysis will be performed using only the observed values without imputation of missing values.

Additional sensitivity analyses will be performed to assess the robustness of primary analysis results. Sensitivity analyses will include the imputation of missing pain intensity scores using different pattern mixture models (PMMs).

A descriptive summary of the weekly averages and the changes from baseline will be generated by treatment group. Graphical displays will be used if appropriate.

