7 TRIAL OBJECTIVES AND ENDPOINTS

The trial objectives and endpoints are given in Section 1.2.

The pain intensity score used for the primary endpoint will be calculated from average pain intensity ratings, assessed once daily in the electronic diary and referring to the CRPS-affected limb. The baseline average pain intensity score is defined as the average of the week before allocation to treatment at Visit 2 and calculated as the average of the 7 average pain intensity ratings starting in the evening of Day -7 until Day -1. A baseline pain intensity score (≥ 4 on the NRS) must be confirmed at the site prior to subject allocation (at Visit 2). Subjects who do not meet eligibility criteria due to inadequate pain (< 4 on the NRS) will be excluded from the trial.

Pain intensity scores from Week 1 through Week 12 will be calculated in a similar manner using average pain intensity ratings obtained from the electronic diary. The Week 12 pain intensity score, for evaluation of the primary outcome, will be the average of up to 7 possible ratings obtained in the 7-day period culminating with the rating obtained in the evening prior to the Week 12 visit.

Handling of missing pain ratings will be addressed in the statistical analysis plan. Compliance with the pain ratings in the electronic diary must be monitored and subjects with insufficient ratings (< 4 ratings per week for 2 weeks) should receive a reminder and undergo re-training.

During Visit 2 (Day 1), Visit 7 (Week 6), Visit 8 (Week 12), Visit 9 (Week 16), and Visit 11 (Week 26), Visit 16 (Week 36), and Visit 17 (Week 52), the subjects will be asked to record the pain intensity ratings for average, worst, and current CRPS-related pain directly on a tablet computer maintained at the site. For subjects included in Treatment Period B, the subjects will also be asked to record pain intensity rating at Visit 12, Visit 13, Visit 14, and Visit 15. Worst and average pain intensity ratings will be based on a 24-hour recall period. The pain ratings and other patient-reported outcomes from the tablet computers recorded up to Week 26 as well as DMA, edema, and PPT assessment will be used for the secondary endpoints.

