9.3 Subject discontinuation from the trial or IMP

Once a subject enrolls in this trial, whilst protecting subject safety, the trial site should make every effort to retain the subject for the planned duration of the trial.

A subject may withdraw consent at any time.

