9.3.1 Subject discontinuation from the trial

All bisphosphonates have a long retention time in bone, and duration of efficacy is related to their persistent effects on bone turnover, specifically the inhibition of activation of bone resorption (Al Nofal et al. 2015; Naylor and Eastell 2012; Jung and Lein 2014). Collection of follow-up data is important for characterizing the safety and efficacy of neridronic acid. Subjects who receive any treatment, even a partial infusion, should be encouraged to remain in the trial for the full duration for follow-up safety and efficacy assessments.

Under certain situations, discontinuation from the trial may be required or be in the best interest of the subject from a risk/benefit perspective. [Table 1](#) lists mandatory and optional reasons for discontinuation from the trial.

Table 1: Reasons for compulsory and optional discontinuation of subjects

Reason	Discontinuation from trial	
	Compulsory	Optional
Enrollment failure (i.e., subject was not allocated to treatment due to failure to meet inclusion or exclusion criteria and did not receive IMP).	X	
Subject withdrawal of consent (the reason for withdrawal must be specified).	X	
Subject death.	X	
Subject loss to follow-up (i.e., no further contact with the subject is possible).	X	
Sponsor decision to discontinue the subject.	X	
Technical reasons (e.g., site is no longer able to function or participate in the trial, and the subject is too remote from other site locations).		X
Sponsor decision to terminate the trial.	X	
Other reasons (e.g., subject becomes engaged in litigation related to their disability from CRPS in which monetary gain may affect their objective participation in the trial).		X

CRPS = complex regional pain syndrome, IMP = investigational medicinal product.

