9.3.2 Subject discontinuation from the IMP

Discontinuation of IMP applies only to Treatment Period A or Treatment Period B. Subjects who are discontinued from IMP should not be discontinued from the trial except for reasons indicated in [Table 1](#). Subjects who are discontinued from IMP should be encouraged to remain in the trial for their own safety and for the integrity of the trial.

Subjects must be evaluated prior to each infusion of IMP. The investigator must permanently or temporarily discontinue treatment with IMP for any reasons listed in [Table 2](#). The investigator may decide to temporarily discontinue a subject from receiving IMP for other reasons (e.g., if further assessments may be helpful to assure safety of the subject). The investigator may also choose to permanently discontinue a subject from treatment if they believe that continued exposure of the subject to neridronic acid may pose an undue risk to the subject, e.g., due to particular adverse events or due to deterioration in the subject's health for reasons related or unrelated to the treatment.

In situations where treatment is temporarily discontinued, Treatment Period A or Treatment Period B may be extended to a maximum of 21 days (for details, see footnote b) in [Section 1.7.1](#) and [Section 1.7.2](#)).

Table 2: Reasons for permanent and temporary discontinuation of subjects from IMP

Reason	Discontinuation from IMP	
	Permanent	Temporary
Symptomatic hypocalcemia.	X	
Serum calcium <7.8 mg/dL (<1.95 mmol/L). The subject may resume treatment following investigator assessment and a repeat serum calcium value above this limit (albumin-corrected serum calcium should be considered if serum albumin is below 3.5 g/dL).		X
Clinical signs of dehydration (e.g., dizziness, palpitations, confusion).		X
Test results suggestive of a possible change in renal function:		

 A persistent ∇25% decrease in the eGFR from the last value observed prior to the first IMP administration, based on repeated central laboratory results from blood samples obtained at least 1 week apart ^a. 	X	

 A ∇25% decrease in the eGFR from the last value observed prior to the first IMP administration. If a repeated measurement of eGFR is within 75% or more of the respective value, the subject may resume treatment ^a. 		X

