12.11 Compliance

Compliance is the adherence to all requirements of the trial protocol.

Trial site compliance will be assured by the implementation of a quality system and the performance of a combination of trial site visits, training, and monitoring visits. Non-compliance should lead to prompt action by the sponsor to secure compliance.

Compliance of the subjects to record their pain intensity assessments in the electronic diary will be checked by the investigator at the respective visits. A non-compliant subject may be withdrawn from the trial at the discretion of the investigator.

Relevant deviations from the protocol will be documented and described in the integrated clinical trial report.

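### Protocol 12.11 lets an investigator withdraw a subject from the whole trial for poor diary compliance, which fits neither the treatment-policy estimand nor the retention rules and causes avoidable missing data

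*Protocol*

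**What the plan says.** Protocol Section 12.11 (Compliance) states: "Compliance of the subjects to record their pain intensity assessments in the electronic diary will be checked by the investigator at the respective visits". The next sentence reads: "A non-compliant subject may be withdrawn from the trial at the discretion of the investigator". The withdrawal is from the trial, not only from study drug. No number of missed entries, warning or re-training step is required first.

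Other parts of the protocol point the other way:

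- **Estimand** (Protocol 1.5.3.1, repeated in 14.1.7.1.1 and SAP 13.1.2): "This treatment policy or de facto estimand measures the effect of neridronic acid regardless of adherence to treatment or protocol".
- **General retention** (Section 9.3): while protecting safety, "the trial site should make every effort to retain the subject for the planned duration of the trial".
- **Treated subjects** (Section 9.3.1): anyone who received even a partial infusion "should be encouraged to remain in the trial for the full duration for follow-up safety and efficacy assessments".
- **After stopping study drug** (Section 9.3.2): "Subjects who are discontinued from IMP should not be discontinued from the trial except for reasons indicated in" Table 1. Table 2 lists serious non-compliance with protocol procedures as a reason to stop study drug permanently. Table 1 does not name diary non-compliance.
- **Low diary compliance** (Section 7): subjects with fewer than 4 ratings per week for 2 weeks "should receive a reminder and undergo re-training".

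**The concern.** A treatment-policy estimand needs outcomes from every treated subject, including those who adhere poorly. Section 12.11 lets poor adherence to one procedure end collection of all outcomes. The decision is discretionary, has no stated threshold, and can differ between sites.

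Three things are at stake. First, Week 12 diary data are lost from subjects who might still have supplied some ratings. Second, data that do not need the diary are lost: Week 12 dynamic mechanical allodynia (DMA), pressure pain threshold (PPT) and edema, Week 26 tablet pain, and safety to Week 52. The first four of these are the whole set of confirmatory secondary endpoints (Protocol 1.5.3.4, SAP 13.2.6). Third, the reasons for missing diary entries may be related to pain, benefit or burden, so the resulting gaps may be informative.

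**Working it through.** **1. Does a poor diary user still contribute?** SAP 13.1.1 averages all ratings available in a week and leaves the weekly score missing only if there are none. One rating in Week 12 therefore gives a Week 12 score. Withdrawal before Week 12 removes that possibility, so the loss is avoidable.

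**2. What does withdrawal cost outside the diary?** Protocol 9.3.3.1 asks, if possible, for one Early Termination Visit with Visit 17 procedures. These include tablet pain, DMA, PPT, edema and safety tests. SAP 19.1.1.9 assigns the data to the nearest scheduled visit, or to the next one if that visit has already taken place. Take a withdrawal at Day 60 after Visit 7. The distance to Day 43 is 17 days and to Day 85 is 25 days. Visit 7 is nearer but done, so the data go to Visit 8 (Week 12). Week 26 and everything later stay missing. At most one assessment is saved. In the 30% responder analyses a missing score counts as non-response (Protocol 1.5.3.2, SAP 13.2.2).

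**3. How long does the rule run?** After Visit 8 the diary is once weekly up to Visit 17 (Protocol 12.3.1.1), and compliance is checked at each later visit. SAP 13.1.1 does not use diary data beyond Day 84 for the primary endpoint. A subject could thus be withdrawn for missed entries that feed no confirmatory endpoint, at the cost of the confirmatory Week 26 value. The Section 7 threshold cannot apply in this phase: a fully compliant subject gives 1 rating per week, which is below 4.

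**4. Illustrative power.** Inputs from Protocol 1.5.1: difference 1.0, SD 2.0, one-sided alpha 0.025, 86 per arm required, 90 per arm planned. The two-sample t test has 2n − 2 degrees of freedom and noncentrality 1.0 / (2.0 × √(2/n)) = √(n/8).

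| n per arm | Lost from 90 | √(n/8) | Power |
|---|---|---|---|
| 90 | 0 | 3.354 | 91.6% |
| 86 | 4 (4.4%) | 3.279 | 90.3% |
| 85 | 5 (5.6%) | 3.260 | 90.0% (0.8999) |
| 81 | 9 (10%) | 3.182 | 88.5% |

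The smallest n with at least 90% power is 86, so the plan's figure reproduces and the sample size calculation is not in error. The extra 4 per arm are assigned to the optional futility look. No dropout allowance is stated, and Section 9.3.3.3 rules out replacement.

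**5. Illustrative bias.** Suppose a share d of the active arm is withdrawn, their true Week 12 mean is s points worse than missing-at-random predicts, and placebo withdrawals follow that assumption. The estimate is then off by about d × s. With d = 10% and s = 1, this is 0.10 × 1 = 0.1 points against the planned 1.0. Over d from 5% to 20% and s from 0.5 to 2, the range is 0.05 × 0.5 = 0.025 to 0.20 × 2 = 0.4. Both inputs are assumptions, and s may be zero.

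**The case against.** The strongest defense is that the passages can be read in sequence: re-train, try hard to retain, and withdraw only as a last resort. Section 12.11 is permissive. The retention rules use *should*, which Protocol 3.2 defines as recommended and not mandatory. Table 1 contains an open, optional row for other reasons that could admit such a withdrawal. Section 7 does not say that withdrawal can never follow re-training. This stands. A reader might infer that 12.11 breaches a binding rule, and the documents do not support that. What does not stand is the sequence itself, because 12.11 neither states it nor refers to Sections 7 or 9.3.

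A reader might also infer that these withdrawals would be missing not at random. Nothing in the documents links diary compliance to pain or benefit, so only *potentially informative* is justified. The plan concedes that missing-at-random cannot be verified and specifies placebo multiple imputation and a delta-shift tipping point (SAP 13.1.3). Those analyses model absent values but cannot recover values that were never collected.

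Thirdly, a reader might take the power figures as the effect of this sentence. They are not. The losses are assumed, and 5 per arm leaves power at essentially the 90% target. The calculation gives a withdrawn subject no weight, although the mixed model uses every observed week. The fair comparison is with a retained subject who fills in the diary badly, not with a complete record. Withdrawal after the Week 12 diary data are complete cannot affect the primary endpoint.

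Finally, 12.11 opens by defining compliance as adherence to all protocol requirements, so the sentence may reach beyond the diary. Simple deletion could therefore remove more than intended and would leave the open Table 1 row untouched.

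**Conclusion.** The point holds as an inconsistency in trial conduct that is cheap to remove. Section 12.11 permits whole-trial withdrawal for a lapse that Section 7 answers with re-training, that Table 2 at its most serious links to stopping study drug, and that the estimand is meant to look past. The clearest loss is visit-based: up to four confirmatory secondary endpoints and later safety data for each subject withdrawn, less at most one salvaged assessment.

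The size cannot be estimated, because the documents give no rate of diary non-compliance or withdrawal. The figures of 91.6%, 90.0% and 88.5% show only that the margin is thin. They rest on the plan's own difference and SD, on assumed losses of 0, 5 and 9 per arm, and on no recovery by the mixed model. No effect on the primary analysis has been demonstrated.

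**What to change.** 1. In Section 12.11, replace the withdrawal sentence. State that poor diary compliance leads to a reminder and re-training and is not by itself a reason for discontinuation from the trial. The subject remains in all scheduled visits unless consent is withdrawn or another Table 1 reason applies.
2. At the other-reasons row of Table 1, add that diary non-compliance alone does not qualify. Otherwise the same withdrawal stays possible by that route.
3. In Section 7, add a compliance criterion for the once-weekly diary after Visit 8, where fewer than 4 ratings per week has no meaning, with the same response of reminder and re-training.
4. Cross-refer Sections 7, 9.3 and 12.11, so that the consequence of diary non-compliance is stated once.

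The subject's right to withdraw and the study-drug discontinuation criteria are unaffected. No analysis or sample size changes. The cost is a few sentences and some extra site follow-up of poorly compliant subjects.

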13 DOCUMENTATION OF TRIAL DATA

The trial documentation must be adequate for the reconstruction of the trial.

13.1 Case report forms

Case report forms for each subject will be provided to the investigator by the sponsor in electronic format to document the trial data.

The investigator and personnel delegated the task will use eCRFs to record information required by the protocol.

All eCRF entries, corrections, and alterations will be made by the investigator or other authorized personnel under their supervision. Entries will be checked against appropriate source documents by authorized sponsor representatives as deemed appropriate in the monitoring guidelines.

The data collection will be done using a validated electronic eCRF system. The collected data will reside on servers of the eCRF provider. Entry, corrections and alterations of data within the system can only be performed by the investigator or other authorized personnel under their supervision and will be captured by the system's audit trail.

Dedicated users (e.g., the investigator, designated persons at the trial site, authorized sponsor representatives, and from other parties involved, e.g., data management) will be trained and receive access rights according to their role in the trial. All users will have access to the system and be able to review their data on an ongoing basis.

After completion of the subject's eCRF, the eCRF must be signed electronically by the investigator. With the investigator's signature it is confirmed that the data in the eCRF are checked, complete, accurate, and in alignment with the source data. Changes to the eCRF after initial signing by the investigator need re-signing.

With database lock, the edit rights to the eCRFs will be removed but the investigator will retain access to view the eCRFs until receipt of a certified copy of all data captured for his or her subjects (site archive). This data will be delivered in a human readable form for retention in his or her files.

13.2 Subject-reported outcomes

Subject-reported outcomes will be collected using a validated electronic patient-reported outcome system including audit trail (electronic diary and site tablet computer).

The investigator will be trained on the use of the electronic patient-reported outcome system and the related oversight system. The oversight system will allow the investigator to review all data entered by the respective site subjects on an ongoing basis.

Subjects will receive a personal electronic diary at the trial site and will be instructed on how to use it.

The tablet computers will be kept at the trial site and subjects will be instructed on how to use it.

No queries will be issued to the investigator for these data, except for clarification of subject identifiers and any operational issues. No queries will be raised to the subject.

With database lock, the writing access to the electronic patient-reported outcome system will be removed. The investigator will receive all data captured for his or her subjects, in a human readable form, on read-only media for his or her files. The information will be provided to the investigator prior to system decommissioning.

13.3 External data

Trial data not recorded in the eCRF or subject-reported outcome, but requested per protocol (e.g., safety laboratory data, ECG data) will be collected and validated via sponsor internal or external data providers. The data integration into the clinical data and respective quality control measures are described in the Data Management Plan.

13.4 Data management

Data management will be performed by sponsor personnel or by authorized sponsor representatives. Documentation of the responsibilities and delegation thereof will be maintained in the trial master file.

All aspects of the data management process, including data validation and query management, medical coding, handling of external data, data lock procedures are described in the Data Management Plan. Details on data validation are described in the Data Validation Plan.

13.5 Source data

Source data is defined by GCP as “all information in original records and certified copies of original records of clinical findings, observations, or other activities in a clinical trial necessary for the reconstruction and evaluation of the trial. Source data are contained in source documents (original records or certified copies)”.

Source data comprise clinical documentation, data, and records (e.g., clinic/hospital records, clinical and office charts, laboratory notes, memoranda, subjects’ diaries or evaluation checklists, pharmacy dispensing records, recorded data from automated instruments, and data and records arising from departments such as the pharmacy, laboratory, and medico-technical departments) that describe or record the methods, conduct, or results of the trial, the factors affecting the trial, and the actions taken.

All source data arising from the trial will be kept by the investigator, who must provide direct access for trial-related monitoring, audits, ethics committee review, and regulatory inspection.

In certain circumstances, data may only be recorded in the trial-specific eCRF and not in other documents. When this occurs, the eCRF is considered to be the source document. Data expected to be only recorded in the eCRF are race/ethnicity and sex.

The nature and location of all source data/clinical documentation will be identified and documented by the investigator to ensure that all sources of original data required to complete the eCRF are known to the sponsor and/or trial site personnel and are accessible for verification during trial-related monitoring, audits, relevant IEC/IRB review, and inspections.

For subject-reported outcomes captured directly via the electronic patient-reported outcome system, source data is defined as the data residing in the vendor’s database.

